The clinical disease under evaluation is pedal onychomycosis. Onychomycosis will be confirmed if fungal hyphae are observed on periodic acid-Schiff (PAS) stain examination of nail plate/bed tissue fragments. The fungal cell wall is composed of layers of chitin, glucan mannoproteins, and glycosylphosphatidylinositol, and the periodic acid-Schiff reaction colors these polysaccharides in the cell walls of fungi magenta. PAS staining of nail clippings is more sensitive than potassium hydroxide (KOH) and fungal culture for the diagnosis of onychomycosis (56). The PAS stain examination will be conducted by a certified microbiology laboratory of the site investigator's choice (their usual and customary practice) or an independent lab that has contracted with the sponsor to conduct the PAS test in support of the investigation. Each site investigator, or the contracted microbiology lab, will forward the results of the PAS tests for each participant. The payment for the baseline PAS stain will be handled by the patient's insurance, in the usual and customary fashion, since this is the typical requirement for standard treatment of mycotic toenails. Once again, anyone randomized to placebo nail solution will receive the active topical nail solution, Tolcylen[™], at the end of the treatment as described elsewhere in this protocol, if the participant desires. The PAS stain examination will be repeated at the termination of the intervention period, at either 3, 7 or 9 months after initiation of the intervention, and will be collected for the purposes of the investigation. As such, PAS assessments after the baseline test are not necessarily part of the clinician's usual and customary practice, since standard therapy usually does not entail a second mycology assessment if therapy has been successful. If, however, nail dystrophy persists, then a follow up PAS stain would be considered a reasonable component of standard therapy. To be fair to our participants, the cost of this final PAS assessment will be covered by the study sponsor. We will also randomly allocate a number of participants to either the active or placebo topical solution even if they do not have a PAS stain positive for fungal elements at baseline, in an effort to ascertain the influence that the active solution might have on non-mycotic dystrophic toenails. The investigation will not be powered a priori to see a statistically significant difference in this secondary analysis.

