It should be noted that the method of supply and application of both the placebo and the active topical nail solution is consistent with the standard method of use approved by the FDA monograph for use of an over-the-counter topical cosmetic agent, in accordance with the existing FDA monograph approved method for the treatment of dystrophic nails (see Tolcylen[™] label, Attachment 1). Participants in each group will be verbally instructed in the proper method of application of the topical solution and will also receive written instructions describing the study regimen and application technique (Attachment 2).

Upon arrival to the clinic for follow-up evaluation and care, the study participant will meet with a blinded investigator in the treatment room. The blinded investigator will review the study protocol and discuss any questions that the participant may have. The blinded investigator will inspect the participant's affected toes and procure the required information (clinical and photographic data) as delineated in this protocol.

Duration of Administration

For participants in both groups, maintenance of topical application of the assigned solution on the mycotic toenail/s will continue for a period of up to 9 (nine) months, for the purposes of the study. This duration of application is based

CONFIDENTIAL

on an average adult nail growth rate of 9 months for emergence from the proximal nail fold to the distal margin of the nail bed. Follow-up inspections will take place at 3, 7, and 9 months, following randomization and initiation of the treatment process. If participant shows clinical and mycological clearance prior to 9 months follow up, the participant may discontinue application of the topical nail solution if desired, in keeping with general clinical practice. The primary efficacy endpoint will occur at the minimum duration of 7-9 months, in keeping with the aforementioned and subsequently reviewed, proposed study timeline.

Timeline

The general design of this study is that of a randomized, controlled trial, wherein the intervention arms of the study consist of the application of either placebo or active topical nail solution, to be performed on volunteer human participants. The proposed study timeline is denoted in Table 2 and Fig. 1, below.

Milestone	Months
Screening visit and enrollment	12
3-month follow up visit	15
7-month follow up visit	18
9-mont follow up visit	21
Data analysis	27
Submit for publication	30

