In the event that a participant withdraws from the study prior to the termination of the designated follow-up period, every attempt will be made to inquire as to the rationale that the participant used in deciding to withdraw. Moreover, permission will be sought to collect at least survival (time to event) data. In light of the importance of complete follow-up, in relation to the integrity of the research study, the following steps will be taken prior to concluding that a participant is definitely lost to follow-up:

- 1. Three separate telephone calls on three separate days, each to the participant's home and place of work.
- 2. A letter sent to the participant's residence via certified mail, asking the individual to contact the study center to discuss their progress and participation in the study.
- 3. A telephone call to the participant's next of kin, to inquire as to the participant's whereabouts and participation in the study.

Statistical Plan

Power and Sample Size Determination

CONFIDENTIAL

Analyzing for the dichotomous outcome, either cured or not cured, using Fisher's exact test for independent groups (active topical nail solution and placebo), in a prospective randomized fashion, expressing the alternative hypothesis as two proportions, at $\alpha = 0.05$, and $\beta = 0.08$, with the event rate in controls as 0.01 and the that in cases as 0.3, and using a 1:1 ratio of cases to controls, we will need 29 participants in each treatment group, or 58 participants overall, to be able to detect a statistically significant difference between the treatment arms. In anticipation of dropouts, limited site enrollment and center effects and multiple center effects (6 clinical sites), an additional 20% will be added in an effort to ensure statistical power. Therefore, a total of 70 participants will be enrolled and randomized, subject to the data safety monitor's surveillance and recommendation.

Statistical Methods

The primary endpoint in this study is the mycological presence or absence of fungal hyphae in fragments of the index toenail as viewed on the microscopic PAS stain, following the application of active topical nail solution, or placebo nail solution, to participant's mycotic toenails.

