Secondary endpoints are changes in the participants' toenail-related quality of life, as measured using the OnyCOE-t[™] quality of life questionnaire (56,57), and changes in the appearance of the index toenail as measured using the visible nail plate involvement score. Additional demographic exposure variables will also be collected and analyzed in order to describe the participants in the study. Specifically, the participant's age, sex, body mass index (BMI), comorbidities and medications, as well as the number of mycotic toe nails, the duration of onychomycosis based on the participant's history, the presence of pedal digital deformity (hammer toe, claw toe, if present), and any local or systemic complication/s that may arise during the course of the investigation.

All participants will be followed to the endpoint of the study, in accordance with the proposed timeline. The data will be considered based on type and distribution. An intention-to-treat analysis will be used, and it will entail descriptive statistical methods, including mean and standard deviation, or median and quartile, to describe demographic variables; as well as tests of the null hypothesis that will include 2-sample Student's *t*-tests, or Wilcoxon rank sum tests, for differences between the two study groups both before and after intervention, and paired *t*-tests, or Wilcoxon signed ranks tests, for comparison of pre- and post-treatment results in single participants, for continuous data, depending on the distribution of the data. The statistician will be blind to treatment allocation, which will be denoted as "A" or "B" until the results are computed, after which time the precise nature of the allocation will be revealed.

CONFIDENTIAL

Participant Population(s) for Analysis

The specific population to be included in this intention-to-treat analysis will be the all-randomized population (any participant randomized into the study, regardless of whether they underwent topical application of active topical nail solution or the placebo). This population will be subjected to primary and secondary endpoint analyses. For any participant lost to follow, their last observation will be carried forward for the subsequent evaluations in accordance with the study timeline.

Safety and Adverse Events

Definitions

Adverse Event

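### At withdrawal the protocol's minimum request is survival data, which no stated endpoint uses, and the final index-nail PAS is not required; a leaver without one has the baseline PAS carried forward

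*Protocol*

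**What the plan says.** Protocol, Data Collection and Follow-up for Withdrawn Participants: sites ask why the participant is leaving, and "permission will be sought to collect at least survival (time to event) data". The section then lists telephone and mail steps before someone is declared lost. It does not name a PAS sample, a nail score or a questionnaire.

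Protocol, Statistical Methods: "The primary endpoint in this study is the mycological presence or absence of fungal hyphae in fragments of the index toenail". The same section continues: "Secondary endpoints are changes in the participants' toenail-related quality of life", together with change in VNPIS. The tests named in the statistical plan are Fisher's exact, t and Wilcoxon tests.

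Protocol, Diagnosis of Primary Outcome: "The PAS stain examination will be repeated at the termination of the intervention period, at either 3, 7 or 9 months after initiation". This is described as one final test, and "the cost of this final PAS assessment will be covered by the study sponsor". The section also allows some participants with a negative baseline PAS to be randomized.

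Protocol, Study Visits and Procedures: five entries (screening, treatment start, months 3, 7 and 9), with no withdrawal visit.

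Protocol, Participant Population(s) for Analysis: the population is everyone randomized, and "For any participant lost to follow, their last observation will be carried forward for the subsequent evaluations". The section When and How to Withdraw Participants applies the same rule to those who choose to stop.

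**The concern.** The withdrawal section sets a floor for what sites must try to obtain, and that floor does not match the trial's outcomes. It asks for a kind of data that no stated analysis uses and leaves out the sample that decides the primary question. Only one post-baseline PAS is planned, so a participant who leaves without it has nothing to carry forward except the baseline result.

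For a baseline-positive participant the outcome is then fixed as not cured, whatever the nail would have shown. True cures in the active arm are counted as failures, the observed difference shrinks and power is lost. For a baseline-negative participant the carried-forward result reads as absence of hyphae, although treatment has shown nothing.

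This cannot be left to the statistical analysis plan. What is requested at withdrawal is settled by the protocol and the consent, and no later analysis can recover a sample that nobody asked for.

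**Working it through.** **1. Match between data requested and endpoints**

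| Item | Needed for a stated endpoint? | In the minimum withdrawal request? |
|---|---|---|
| Index-nail PAS | Yes, primary | No |
| OnyCOE-t | Yes, secondary | No |
| VNPIS | Yes, secondary | No |
| Survival (time to event) | No | Yes |

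**2. Outcome of a leaver under the carry-forward rule**

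- Has an end-of-intervention PAS (month 3, 7 or 9): that result is carried forward.
- Has none, baseline positive: scored not cured.
- Has none, baseline negative, and included in the all-randomized analysis: scored hyphae absent.

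**3. The plan's own sample size**

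Inputs from Power and Sample Size Determination: rates 0.01 and 0.30, α = 0.05, 1:1 allocation, 29 per arm, plus 20% to reach 70. Sidedness is not stated. The two-sided normal-approximation formula with continuity correction at 80% power gives 30 per arm, against the stated 29. Exact two-sided Fisher power at 29 per arm is 0.843. The inflation is 58 × 1.20 = 69.6, rounded up to 70, or 35 per arm.

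**4. Power when every leaver lacks a final PAS**

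Let a share d of each arm leave, all baseline-positive and all scored not cured, while the rest have the planning rates. The protocol gives no dropout rate, so d is assumed. One-sixth is about the share implied by the margin if all of it went to dropout (12/70 = 17%). The observable rates are:

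- active = 0.30 × (1 − d)
- placebo = 0.01 × (1 − d)

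| d (assumed) | Active | Placebo | Exact two-sided Fisher power, 35 per arm |
|---|---|---|---|
| 0 | 0.300 | 0.0100 | 0.935 |
| 0.10 | 0.270 | 0.0090 | 0.886 |
| 1/6 | 0.250 | 0.0083 | 0.839 |
| 0.20 | 0.240 | 0.0080 | 0.810 |
| 0.30 | 0.210 | 0.0070 | 0.701 |

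The loss at d = 1/6 is 0.935 − 0.839 = 0.096. That is the most a fix could recover, because the 0.935 benchmark gives leavers the full planning cure rates.

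**5. What a PAS taken at withdrawal would recover, d = 1/6**

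Let r be the active cure rate among leavers at the time they leave (assumed), with placebo kept at 0.01. The active rate becomes 0.30 × 5/6 + r × 1/6.

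| r (assumed) | Active rate | Power | Gain over 0.839 |
|---|---|---|---|
| 0.05 | 0.258 | 0.851 | 0.012 |
| 0.10 | 0.267 | 0.873 | 0.034 |
| 0.15 | 0.275 | 0.892 | 0.053 |

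**The case against.** The strongest objections are these.

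- **Not every leaver is affected.** A reader might infer that each early leaver's primary outcome is simply the baseline PAS. The text does not support that. The repeat PAS is tied to the end of the intervention at month 3, 7 or 9, so someone who stops at one of the earlier visits can have a post-baseline result. Duration of Administration also foresees earlier mycology: "If participant shows clinical and mycological clearance prior to 9 months follow up", application may stop. This stands, and the point is confined to those who leave without that sample.
- **A floor is not a ban.** A reader might also infer that the protocol gives up the PAS. The request is worded as a minimum, so a site may take a clipping from a willing leaver, and the protocol stresses complete follow-up. This stands too. Even so, the floor is all that sites are told to seek, and the primary outcome is not in it.
- **The full power loss overstates the benefit.** The protocol puts replacement of the visible nail at about 7 to 9 months, so an early sample would be expected to show fewer cures than 30%. This is right, and step 5 of the working allows for it. Only return visits at month 9 could approach the full gain.
- **The margin absorbs it.** Power of 0.839 with one-sixth leaving is practically the 0.843 available at 29 per arm. This is correct under these assumptions, although the same 20% is also meant to cover limited site enrollment and center effects.
- **No false-positive risk is shown.** Scoring baseline-positive leavers as not cured does not by itself favor the active arm. Nothing here shows inflated type I error, and none is claimed.

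**Conclusion.** The point holds in limited form. The minimum request at withdrawal names data that no stated endpoint uses and does not require the final PAS. A participant who leaves without an end-of-intervention PAS is therefore analyzed on the baseline result: not cured if positive, hyphae absent if negative and included.

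The cost is moderate. At one-sixth leaving, power falls by at most about 10 points (0.935 to 0.839); at 20% leaving it is 0.810. A sample taken at withdrawal would realistically return about 1 to 5 points at one-sixth leaving. These figures assume equal dropout in both arms, all leavers baseline-positive and without a final PAS, planning rates among those who stay, and a two-sided test. The dropout shares and the 5% to 15% cure rates at withdrawal are assumptions, not protocol figures.

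The trial is not broken by this: power stays above 80% up to 20% leaving. The change should still be made, because following the text as written loses primary-outcome data that could be had cheaply.

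**What to change.** In Data Collection and Follow-up for Withdrawn Participants, replace the survival wording with: *at least a final index-nail PAS sample, VNPIS with photograph, and OnyCOE-t, where the participant agrees, at withdrawal or preferably at the scheduled month-9 date*. Add that samples taken before month 9 are flagged, and that a withdrawal PAS is used only where the month-9 PAS is missing.

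The cost is one replaced sentence and a short rule, plus reuse of an existing follow-up case report form. The sponsor already covers one final PAS per participant; where both a withdrawal and a month-9 sample are taken, the second would be an extra test. The downsides are that some PAS results will come before month 9, and that the yield depends on leavers agreeing.

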Number of Participants	Analyzing for the dichotomous outcome, either cured or not cured, using Fisher's exact test for independent groups (active topical nails solution alone versus placebo nail solution), in a prospective randomized fashion, expressing the alternative hypothesis as two proportions, at $\alpha = 0.05$, and $\beta = 0.80$, with the event rate in controls estimated to be 0.01 and the event rate in cases estimated to be 0.3, and using a 1:1 ratio of cases to controls, 29 participants will be needed in each treatment group in order to identify a statistically significant difference, should one exist. In anticipation of dropouts, limited site enrollment, and center effects and multiple center effects (≥6 clinical sites), an additional 20% will be added in an effort to ensure statistical power. Therefore, a minimum of 70 participants will be enrolled and randomized, subject to the data safety monitor's surveillance and recommendation.
Diagnosis and Main Inclusion Criteria	The main clinical disease under evaluation is toe onychomycosis. Participants will be males and non-pregnant females 18 years of age or older that have been diagnosed with distal subungual onychomycosis (DSO) involving at least one toenail. Diagnosis of this condition is to be made on the basis of history, physical examination, and a mycological inspection that includes a tissue examination for fungal hyphae (PAS stain). Evidence of fungal hyphae will be considered a positive confirmation of the diagnosis of toenail onychomycosis.
Study Product and Regimen	All participants will be randomized to either the active topical nail solution group, antifungal solution treatment, or to the placebo nail solution group. The topical antifungal medication under investigation is Tolcylen [™] . It will be provided by Marlinz Pharma, Houston, TX, the study funding Sponsor. The topical therapy will be applied in accordance with the existing FDA-approved method for use of this cosmetic agent.
Duration of administration	Administration of the interventions, active and placebo, will continue for no longer than nine (9) months. Administration of the topical agent may stop sooner if clinical and mycological evidence of cures are identified prior to nine (9) months.

CONFIDENTIAL

ponson marine i narina	

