Reference therapy	Participants in the control group will apply a placebo topical solution to the involved toenail/s. Preparation of the placebo solution, dimethicone 5%, was undertaken with the aim of making it as close as possible to the active topical nail solution in terms of color and texture, and other physical characteristics. The placebo nail solution, like the active topical nail solution, meets the FDA's safe ingredient criteria for an over-the-counter topical agent. The placebo, like the active topical nail solution, will be supplied in three (3) 7.5 ml tubes with a controlled-release applicator mechanism that allows thin coat of the solution to be applied at a time, and the instructions for application specify that only thin coat of solution to be applied daily to under the leading edge, borders of the toenail and the entire surface of the toenail.
Statistical Methodology	All participants will be followed to the endpoint of the study, in accordance with the proposed timeline (see below). An intention to treat analysis will be used. Data analysis will entail descriptive statistical methods, including mean and standard deviation, or median and quartile, to describe demographic variables; as well as inferential statistical methods that will include two sample tests of the null hypothesis for differences between the two treatment groups both before and after active topical nail solution or placebo application, and for comparisons of pre-treatment and post-treatment results in single participants, for mycological tests and outcomes. The Wilcoxon rank sum (Mann Whitney) test for unpaired data will be used to identify differences between the two intervention groups both before and after active topical nail solution or placebo application, and the Wilcoxon signed rank test for paired data will be used for comparison of pre-treatment and post-treatment results in single participants, mycological tests, and the OnyCOE-t [™] and Visible Nail Plate Involvement Scores. Participants will be analyzed as randomized, and the last observation carried forward method will be used if a participant fails to complete the study protocol (lost to follow up for any cause, whether at-random or otherwise). The participants, as well as all observers and outcomes assessors, will be blind to

CONFIDENTIAL

Research Protocol

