Table 1 Topical solution tube site-participant designation*

CONFIDENTIAL

A4	B4	C4	D4	E4	F4	G4	H4	J4
A5	B5	C5	D5	E5	F5	G5	H5	J5
A6	B6	C6	D6	E6	F6	G6	H6	J6
A7	B7	C7	D7	E7	F7	G7	H7	J7
A8	B8	C8	D8	E8	F8	G8	H8	J8
A9	B9	С9	D9	E9	F9	G9	H9	J9
A10	B10	C10	D10	E10	F10	G10	H10	J10
An	Bn	Cn	Dn	En	Fn	Gn	Hn	Jn

*This designation correlates with the randomization schedule and enables the principal investigator to keep track of active and placebo distribution and use.

A study coinvestigator, not participating at a study site, and not tasked with data analyses, will maintain the random allocation code, which will contain this same information as well as the randomly allocated topical solution, denoted as either the placebo nail solution or the active topical nail solution.

Inclusion and Exclusion Criteria

Inclusion criteria for participation in this study include:

- 1. Male or female participants aged 18 years or older;
- 2. If female is of childbearing potential, she must not be pregnant at the time of enrollment and she must be using an accepted form of birth control during the study treatment period (acceptable forms include: postmenopausal, surgical sterility, complete abstinence, sterilized sexual partner, tubal occlusion, copper-T intrauterine device, levonorgestrelreleasing intrauterine device, medroxyprogesterone injections, etonogestrel implants, combined pills, norelgestromin/ethinly estradiol transdermal system, intravaginal device, or Cerazette pill; and for males the use of a condom with spermicide or surgical sterility);
- 3. Participant has a diagnosis of onychomycosis diagnosed by means of history, physical examination, and positive (evidence of fungal hyphae) mycological tissue examination by periodic acid-Schiff (PAS) staining;
- 4. At least one toe nail with distal subungual involvement, localized to any toe, with at least 10% involvement and including up to 100% involvement of the visible nail plate, any nail plate thickness, with the index nail being the most involved per inspection by the on-site investigator and agreed upon by the designated co-investigator study doctor ([name], DPM), who will inspect specific clinical photographs of the involved nail/s (the photographs will be obtained at each study site using a specified method, as demonstrated to site investigators, so that the clinical features are appropriately demonstrated);

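### The planned between-arm tests of VNPIS and OnyCOE-t ignore the baseline score already collected, so both secondary comparisons are less precise than they need be

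*Protocol*

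**What the plan says.** Protocol, Statistical Methods, defines the secondary endpoints as changes: in toenail-related quality of life (OnyCOE-t) and in the appearance of the index nail (VNPIS). For continuous data it then names two kinds of test:

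- two-sample t or Wilcoxon rank sum tests "for differences between the two study groups both before and after intervention";
- paired t or Wilcoxon signed rank tests of pre- against post-treatment values within participants.

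The Statistical Methodology entry of the Study Summary gives the same structure. The rank sum test is used "to identify differences between the two intervention groups both before and after active topical nail solution or placebo application", and the signed rank test is assigned by name to OnyCOE-t and VNPIS. The Methodology entry of the Study Summary also describes quality of life as analysed in a paired, single-subject way.

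Both scores have a baseline. The VNPIS section has the nail scored at baseline and at every follow-up visit. The Quality of Life Assessment section uses OnyCOE-t before, during and after the intervention, and to compare the study groups. The protocol nowhere describes a between-arm estimate that adjusts for the baseline score.

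**The concern.** The Objectives section sets a comparative secondary aim: the effect of the two arms on quality of life. Three features of the named tests serve that aim poorly.

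- **The post-treatment between-arm test ignores baseline.** Inclusion criterion 4 admits nails with 10% to 100% involvement and any thickness, so participants may start far apart. With about 35 per arm, the arms can differ at baseline by chance, and an unadjusted comparison carries that difference forward in proportion to r.
- **The baseline between-arm test has no use.** Randomisation makes its null hypothesis true, so about 5% of such tests are significant by chance, and none improves the treatment estimate.
- **The paired tests answer another question.** They ask whether scores moved within participants, not whether they moved more on active than on placebo.

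At stake is the precision of the VNPIS and OnyCOE-t comparisons, and how clearly they can be read.

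**Working it through.** **1. The plan's own figure.** The protocol gives no sample size or power for VNPIS or OnyCOE-t. Its only calculation is for the binary cure endpoint: Fisher's exact test, "with the event rate in controls estimated to be 0.01 and the event rate in cases estimated to be 0.3", 1:1 allocation, giving "29 participants in each treatment group, or 58 participants overall". Exact two-sided Fisher power at these rates is 81.9% with 28 per arm and 84.3% with 29, and it stays above 80% from 28 on. So 29 is reproduced to within one participant per arm at 80% power. The 20% addition gives 58 × 1.2 = 69.6, or 70. (β is printed as 0.80 in the Study Summary and 0.08 in the Power section. That needs reconciling but does not bear on this point.)

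**2. Precision.** Let r be the correlation between a participant's baseline and nine-month score, with equal SDs at both times. Relative to the unadjusted post-treatment comparison (variance = 1), the between-arm difference has variance:

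- change score: 2(1 − r)
- ANCOVA: 1 − r²

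Since 1 − r² = (1 − r)(1 + r), ANCOVA is never worse than either alternative when r is known. A change-score test is worse than post-only when r is below 0.5.

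The protocol gives no r, SD or expected effect for either score, so r is an assumed range. Power uses an illustrative true difference of 0.5 SD and the normal approximation Φ(0.5/√(2(1 − r²)/n) − 1.96) with n = 35 per arm. The unadjusted test has power 55%.

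| Assumed r | ANCOVA variance | Change-score variance | Variance saved by ANCOVA | 70 adjusted participants equal, unadjusted | Power with ANCOVA |
|---|---|---|---|---|---|
| 0.2 | 0.96 | 1.60 | 4% | 70/0.96 = 73 | 57% |
| 0.3 | 0.91 | 1.40 | 9% | 70/0.91 = 77 | 59% |
| 0.5 | 0.75 | 1.00 | 25% | 70/0.75 = 93 | 68% |
| 0.6 | 0.64 | 0.80 | 36% | 70/0.64 = 109 | 74% |
| 0.7 | 0.51 | 0.60 | 51% | 70/0.51 = 137 | 83% |

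Estimating the slope costs a little. It multiplies the ANCOVA variance by about 1 + 1/(2n − 4) = 1 + 1/66 = 1.015. Adjustment breaks even where r² = 1 − 1/1.015 = 0.015, that is, r about 0.12.

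**3. Chance imbalance.** The standard error of the baseline difference between arms is √(2/35) = 0.24 SD. An imbalance of that size shifts the unadjusted post-treatment difference by r × 0.24 SD: 0.05 SD at r = 0.2, 0.12 SD at r = 0.5, 0.17 SD at r = 0.7. This is the same loss as in step 2, seen in a single trial. It is not a bias over repeated trials.

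**4. What within-arm tests can show.** Paired t-tests were simulated in two arms with the same true change, so with no treatment effect. There were 29 or 35 per arm, r of 0.5 or 0.7, common changes of 0 to 0.8 SD, and 10,000 runs per setting. The chance that only the active arm was significant was about 5% with no change, peaked near 25% at moderate change, and fell to near zero at large change. The chance that exactly one arm was significant peaked near 50%. The post-treatment between-arm test stayed at about 5% throughout.

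**The case against.** The strongest reply is that the comparison that matters is already planned. A two-sample test after treatment is named twice, and it holds its type I error. That stands. A reader might infer from the emphasis on before/after and paired tests that no between-arm comparison exists, or that the analysis is invalid. The protocol supports neither inference, and the point is one of efficiency.

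A reader might also infer that significance in the active arm alone will be presented as superiority over placebo. No such rule appears, and the stated aims are comparative. Step 4 shows only why paired tests should be labelled descriptive.

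A further tempting argument is regression to the mean, because the index nail is chosen "with the index nail being the most involved per inspection by the on-site investigator". The protocol does not bear this out. Picking the worst nail does not select participants with extreme OnyCOE-t scores. For VNPIS, the reported intra-rater correlations of 0.8768 to 0.9687 suggest little scoring noise, entry has no high severity threshold, and a co-investigator must agree the choice from photographs.

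It can be said that covariates for unpowered secondary endpoints belong in a statistical analysis plan, and that wording the endpoints as changes leaves room for a two-sample test of change. The second point has some force, since the text is loose. But the protocol does not leave the choice open: it names the tests, and none uses baseline as a covariate. A change-score reading would not cure this, and below r = 0.5 it would be less precise than the post-only test.

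Finally, r is unknown, and it could be low if cleared nails cluster near the VNPIS floor of 7. That stands, and is why the range goes down to 0.2.

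**Conclusion.** The point holds as one of precision and clarity for the secondary endpoints. The planned post-treatment test is valid but discards the baseline score. The baseline tests are uninformative, and the paired tests do not compare the arms.

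The direction of the loss is certain for any r above about 0.12. Its size is not: about 4% of variance at r = 0.2, 25% at 0.5 and 51% at 0.7, assuming a roughly linear relation with equal SDs. The primary PAS endpoint and N = 70 do not change. The change is worth making because the data are already planned, but nothing here undermines the trial's main conclusion.

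**What to change.** In Statistical Methods, and to match in the Study Summary:

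1. For nine-month VNPIS, and for each OnyCOE-t scale that has a baseline value, make the between-arm analysis an ANCOVA with arm and the participant's baseline score. Report the adjusted difference with a 95% CI. Any scale without a pre-treatment value, as may be the case for treatment satisfaction, is compared unadjusted.
2. Name rank ANCOVA as the fallback if the distribution is poor. VNPIS is bounded at 7 and 27, so this should be settled in advance.
3. Drop the baseline significance tests and describe baseline by arm.
4. Keep within-arm changes as descriptive summaries.

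The cost is one degree of freedom per model and a few lines of wording. No new visits, measurements or participants are needed. The wording should be fixed before the allocation is revealed.
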